The protocol, informed consent form(s), recruitment materials, and all participant materials will be submitted to the IRB for review and approval. Approval of both the protocol and the consent form must be obtained before any participant is enrolled. Any amendment to the protocol will require review and approval by the IRB before the changes are implemented to the study. All changes to the consent form will be IRB approved; a determination will be made regarding whether a new consent needs to be obtained from participants who provided consent, using a previously approved consent form.

1 PROTOCOL SUMMARY

1.1 SYNOPSIS

Title: PAZAZ: Personalized azithromycin/metronidazole, in combination with standard induction therapy, to achieve a fecal microbiome community structure and metagenome changes associated with sustained remission in pediatric Crohn's Disease (CD)-- a pilot study

Study Description: This is a multi-center, randomized, controlled open-label add-on design trial pilot study to evaluate the efficacy of personalized adjunctive antibiotic (azithromycin + metronidazole) therapy in pediatric subjects with mild to moderate Crohn's disease (CD) who have a relapse-associated microbiome profile. The study hypothesis is that adjunctive antibiotic therapy will improve clinical response to standard of care (SOC) induction therapy in a subgroup of CD patients with a relapse-associated microbiome profile. This is an add-on design trial for subjects already receiving SOC induction therapy; there will be no placebos.

Prior to starting SOC induction therapy at week 0, subjects will provide a baseline stool sample that will be screened for microbiome profiles associated with risk of relapse according to an established statistical model.

At week 4, subjects with a relapse-associated microbiome will be randomized into either a control arm that will continue to receive SOC induction therapy for an additional 8 weeks, or a treatment arm that will receive adjunctive antibiotic therapy in addition to continuing to receive SOC induction therapy for an additional 8 weeks. Subjects who do not have a relapse-associated microbiome will enter a separate control arm that will continue to receive SOC induction therapy and will have data collected for exploratory objectives. Subjects who are not in clinical

remission by week 4 will receive antibiotic therapy regardless of microbiome signature at baseline. Subjects will be monitored for an additional 40 weeks after the treatment period (52 weeks total).

Objectives:	
Primary Objective: To evaluate the potential efficacy of personalized adjunctive antibiotic therapy in maintaining remission in pediatric subjects undergoing SOC induction therapy for mild to moderate Crohn's disease.
 
Secondary Objective: To evaluate longitudinal (clustered and with respect to baseline) changes in disease activity indices (PCDAI) components and inflammatory markers in stool and blood.
 
Exploratory Objectives: To investigate relationship between changes in subject microbiome composition and changes in disease activity over time.

Outcome variables:	
Primary Outcome variable: Sustained remission defined as no need of re-induction for clinical flare (new course of nutritional therapy, need to start steroids), steroid dependence, biologic (anti-TNF) use, and/or intestinal surgery by 12 months.
 
Secondary Outcome variables: Longitudinal (clustered and with respect to baseline) changes in disease activity indices (PCDAI: 0-100) components and inflammatory markers in stool and blood at each study visit up to 12 months. Longitudinal (clustered and with respect to baseline) changes in patient-reported outcomes (PRO) by 12 months.
 
Exploratory Outcome variable: Longitudinal (clustered and with respect to baseline) changes in fecal microbiome taxonomic composition or in total gene (metagenome) content. The changes will be analyzed for association with changes in disease activity (e.g. relapse or sustained remission) over time up to 12 months.

Study Population:	Children aged 3 to 17 years (inclusive) with mild to moderately active Crohn's disease who will receive standard of care induction therapy.
Phase:	2
Description of Sites/Facilities Enrolling Participants:	
This is a multi-center trial with eight participating sites in Canada, the U.S.A. the Netherlands, and Israel. The sites are pediatric gastroenterology clinics located at:
 
1. Dalhousie University, IWK Health Centre, Halifax, Nova Scotia (Canada)2. University of California San Francisco, Benioff Children's Hospital, San Francisco, CA3. University of Pittsburgh Medical Center, Children's Hospital of Pittsburgh, Pittsburgh, PA4. Amsterdam University Medical Centers, Academic Medical Center. Amsterdam, The Netherlands

[figure not shown]
5. Wolfson Medical Centre, University of Tel Aviv, Tel Aviv, Israel

Description of Study Intervention: Antibiotics will be administered orally for an 8-week period. Azithromycin will be administered at a dose of 7.5mg/kg to a maximum of 500mg/day for 5 consecutive days per week for the first 4 weeks and then 3 consecutive days/week for 4 weeks. Metronidazole will be administered 10mg/kg twice daily to a maximum of 1000mg/day for 8 weeks.

Study Duration: 3 years

Participant Duration: The duration of study participation is 52 weeks (12 months)

1.2 SCHEMA

*see text 4.1 for guidance

1.3 SCHEDULE OF ACTIVITIES (SOA)

Procedures	Visit 1 Screening ≤30 days prior to week 0	Visit 2 Week 0	Study Visit 3 Week 4	Study Visit 4 Week 12	Study Visit 5 Week 24	Study Visit 6 Week 36	Final Study Visit 7 Week 52
Informed consent	X						
Demographic data	X						
Medical history	X	X	X	X	X	X	X
Review inclusion/exclusion criteria	X	X					
Concomitant medication review	X	X	X	X	X	X	X
Physical exam (including height and weight)	X	X	X	X	X	X	X
Medication calendar distribution and teaching		X					
Blood sample ^a	X	X ^b	X	X	X	X	X
Calculate PCDAI score (0-100)	X	X ^b	X	X	X	X	X
Stool sample (16S rRNA)	X	X ^b	X	X	X	X	X
Stool sample (FCP)	X	X ^b	X	X	X	X	X
Stool sample (C. difficile infection testing) ^c	X						
Urine pregnancy test ^d	X		X				
Adverse event review and evaluation			X	X	X	X	X
Randomization			X				
ECG, if applicable ^e			X				
Administer antibiotic, if applicable			X				
Teaching for antibiotic medication calendar, if applicable			X				
Complete Case Report Forms (CRFs)	X	X	X	X	X	X	X
IMPACT (ages 9 and older)		X		X	X		X

A window of study timepoint +/- 5 days is allowed for all visits/questionnaires/sampling.

a: Includes hematology and clinical chemistry Albumin, C reactive protein (CRP), hematocrit (HCT), erythrocyte sedimentation rate (ESR), alanine transaminase (ALT), aspartate transaminase (AST), creatinine, and bilirubin. Total blood volume collected at each visit will be 5ml.

b: The timing of the Screening and Week 0 visits will depend on the start of therapy. Week 0 blood and stool samples will not be repeated if provided during the screening visit, provided that the stool samples were collected prior to bowel prep.

c: If performed for clinical indication, as per standard of care

d: Only applicable for post-menarchal female participants initiating methotrexate

Procedures	Visit 1 Screening ≤30 days prior to week 0	Visit 2 Week 0	Study Visit 3 Week 4	Study Visit 4 Week 12	Study Visit 5 Week 24	Study Visit 6 Week 36	Final Study Visit 7 Week 52
e: All patients randomized to group A2 and C will receive an ECG exam both prior to and at 2-4 weeks after the initiation of the study drug							

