2.3.3 ASSESSMENT OF POTENTIAL RISKS AND BENEFITS

The available information suggests that the present clinical study has an acceptable risk-benefit ratio.

Approximately 50% of pediatric patients with CD will relapse within a year of starting induction therapy and require repeated courses of induction therapy and/or treatment escalation.^{41,42} Subjects in the antibiotic treatment arm of this trial will continue to receive standard therapy and are at comparable risk of relapse as subjects in the control arms. In group C of subjects not achieving remission with nutritional induction therapy alone, there will be no randomization and antibiotics will be given as additional induction treatment. The patient, parents and treating physician are free at all times to choose any treatment outside of the study.

The risk of rare, but serious, heart-related side effects from the antibiotic drug azithromycin are minimized by screening patients for heart rhythm irregularities prior to administering antibiotics. Metronidazole presents minimal risk to the subjects and is routinely used in this pediatric population. The safety monitoring practices employed by this protocol are adequate to protect the subjects' safety and detect all anticipated adverse events.

Subjects in the antibiotic intervention arm may experience direct health benefit through the study treatment by reducing their risk of disease flare thus avoiding additional intestinal damage as well as additional immune suppression or surgery. There will be no additional direct benefit for subjects in the reference arms because they will be receiving standard care. The knowledge gained from this trial could lead to improved treatment approaches for a subgroup of patients who have a relapse-associated microbiome profile.

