5.2 EXCLUSION CRITERIA

An individual who meets any of the following criteria will be excluded from participation in this study:

1. Current or previous use of anti-TNF or other biologic therapy
2. Presence of stricturing, penetrating (intestinal or perianal) and/or fistulizing CD.
3. Pregnancy or lactation
4. Have undergone intestinal resection
5. Laboratory diagnosis of Clostridium Difficile Infection (CDI), if performed for clinical indication
6. Treatment with another investigational drug or other intervention within 30 days before week 0
7. Risk factors for arrhythmia including history of prolonged QTc, hypokalemia or hypomagnesemia, resting bradycardia, or concurrent treatment with other drugs with potential for QT prolongation.
8. History of Cockayne syndrome
9. Prior diagnosis of any hematologic condition/blood dyscrasia which may result in leukopenia (even if leukocyte count is normal at screening)
10. Known allergy or intolerance to azithromycin or metronidazole
11. Subjects who received IV anti-infective within 35 days prior to week 0 visit or oral anti-infectives within 14 days prior to the week 0 visit.
12. Subject on oral aminosalicylates who has not been on stable doses for greater than, or discontinued within, at least 14 days prior to week 0.
13. Subject on cyclosporine, tacrolimus or mycophenolate mofetil. Stable doses (no change within 14 days prior to week 0) of Azathioprine, 6-mercaptopurine or MTX are not a reason for exclusion.
14. Subject who received fecal microbial transplantation within 35 days prior to week 0 visit.
15. Screening laboratory and other analyses show any of the following abnormal results:
 - AST, ALT > 2 X upper limit of the reference range (as determined locally at each site)
 - Urea, Creatinine > 1.5X upper limit of the reference range (as determined locally at each site)
 - White blood cell (WBC) count < 3.0 X 10⁹/L
 - Total bilirubin >= 20 micromol/liter (1.17mg/dl); except for subjects with isolated elevation of indirect bilirubin relating to Gilbert syndrome
 - Hemoglobin < 80 gram/liter
 - Platelets < 100,000/ μ L

Note: The laboratory markers of e.g. AST and ALT are deliberately specified relative to upper limit of normal as these values (and units used) differ between the different labs within the USA and across the study sites in the USA, Canada and Europe.

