8.2 SAFETY AND OTHER ASSESSMENTS

Electrocardiograms (ECGs): ECG is for screening purposes only to identify prolongation of QT (QTc) corrected for age appropriate norms. If there is prolongation, as identified by each responsible physician, then the responsible physician is responsible for communicating this finding with the patient and family and arranging appropriate follow-up with cardiology. Patients found to have QT prolongation will not be treated with investigational therapy and appropriate guidance will be given regarding avoiding other medication with the potential of QTc prolongation (e.g. avoiding ondansetron). Further, all patients randomized to group A2 will receive a follow-up ECG 2-4 weeks after the initiation of the study drug to ensure that new-onset QT prolongation is not occurring as a result of azithromycin treatment. If clinically significant QT prolongation is detected at follow-up ECG, patients should discontinue investigational therapy. If the subject is not in clinical remission at week 4, then the responsible physician will decide whether azithromycin/metronidazole can be started as additional induction therapy.

Blood samples: Blood drawn as per the standard of clinical care will be tested for alanine transaminase (ALT), aspartate transaminase (AST), bilirubin, BUN and Creatinine by the local clinical labs to monitor for toxicity due to methotrexate.

Urine pregnancy tests: A urine pregnancy test will be administered at screening and repeated at week 4 prior to the initiation of methotrexate in post-menarcheal female patients. These tests will be used to prevent exposure of participants to potential embryotoxic/teratogenic effects of methotrexate. Counselling and reinforcement of these potential risks and the importance of pregnancy prevention will be included at every study visit. Post-menarcheal patients will be counselled about the use of birth control to prevent unplanned pregnancy while taking methotrexate during this study period.

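### Nothing between week 0 and opening the envelope re-checks eligibility, and the only ECG follows allocation, so a child barred by QT prolongation can be found in A2 but not by ECG in A1

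*Combined protocol and SAP*

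**What the plan says.** **Eligibility.** Exclusion 7 (section 5.2) covers "Risk factors for arrhythmia including history of prolonged QTc, hypokalemia or hypomagnesemia, resting bradycardia, or concurrent treatment with other drugs with potential for QT prolongation". In the Schedule of Activities (section 1.3) the row "Review inclusion/exclusion criteria" is marked at screening and week 0 only. Medical history and concomitant medication are reviewed at every visit, including week 4.

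**ECG.** The row "ECG, if applicable ^e" has one mark, at week 4, which is also the randomisation visit. Footnote e defines who is tested by the group they are in: "All patients randomized to group A2 and C will receive an ECG exam both prior to and at 2-4 weeks after the initiation" of study drug. Section 8.2 gives the purpose: "ECG is for screening purposes only to identify prolongation of QT (QTc) corrected for age appropriate norms". It also gives the consequence: "Patients found to have QT prolongation will not be treated with investigational therapy". For the later ECG, section 8.2 names one group: "all patients randomized to group A2 will receive a follow-up ECG 2-4 weeks after the initiation of the study drug". Section 2.3.3 relies on "screening patients for heart rhythm irregularities prior to administering antibiotics", which places the check before the drug but not before randomisation.

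**Allocation.** In section 6.3 the family opens the envelope, the physician learns the result, and a prescription follows. No eligibility or ECG step is placed before the envelope.

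**Analysis.** Under section 9.3, ITT holds all randomised children. The mITT set needs at least 48 hours of antibiotic (and six months of outcome data), and the per-protocol set at least two weeks of study intervention. Section 9.4.2 uses ITT for the primary analysis and mITT as a sensitivity analysis. Section 7.1 moves children who stop antibiotics to A1 care, leaves them out of the A1 analysis and reports them separately.

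**The concern.** Anything that decides whether a child can receive the randomised treatment should be settled before allocation, and in the same way for both arms. Here four weeks pass between the last eligibility review and randomisation. A child's standing under exclusion 7 can change in that time, for example by starting a QT-prolonging drug. An unknown prolonged QTc comes to light only if the child is allocated to A2 (or placed in the non-randomised Group C).

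Three things are at stake. The primary comparison loses contrast, because an untreated child counts as treated by assignment. The sets defined by antibiotic intake lose such children from one arm of an open-label trial. And the addendum's feasibility measure, the share of enrolled children who are randomised following the microbiome result, records a child who cannot take the allocated treatment as a success. The addendum foresees no substantial change to the protocol if the pilot proves feasible, and possible inclusion of pilot data in the full trial, so the gap would carry forward.

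**Working it through.** **1. Follow one child through the text.** Take a Group A child in remission at week 4, with no relevant history, whose ECG would show QT prolongation.

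| Step | Allocated to A2 | Allocated to A1 |
|---|---|---|
| Criteria review, screening and week 0 | passes | passes |
| Criteria review, week 4 | none marked | none marked |
| Envelope opened (6.3) | yes | yes |
| Pre-treatment ECG (footnote e) | yes, prolongation found | none planned |
| Antibiotics (8.2) | barred | not applicable |
| ITT | kept, untreated | kept |
| mITT and per-protocol | lost | not removed on this ground |
| Feasibility: randomised | success | success |

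Read literally, the mITT set admits no A1 child, since none takes antibiotics. On any reading that admits A1, the barred child is lost from A2 only. Section 9.4 assigns no analysis to the per-protocol set.

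Section 7.1 speaks of stopping antibiotics, so a child who never starts is not clearly covered. A child stopped after the follow-up ECG is covered, and reporting that child separately sits awkwardly with ITT.

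**2. Reproduce the plan's own figure.** Section 9.2 states 25 per arm for the larger trial: flare risk 80% against 40%, 80% power, 10% dropout; section 9.4.1 sets two-sided 0.05.

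- Pooled normal formula: n = [1.96√(2 × 0.6 × 0.4) + 0.8416√(0.8 × 0.2 + 0.4 × 0.6)]² / 0.4² = 22.3, so 23; 23/0.9 = 25.6, so 26.
- Arcsine formula: 22; 22/0.9 = 24.4, so 25.

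The stated 25 is reproduced and is not in dispute.

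**3. Chance of at least one barred child in A2.** The rate q of QT prolongation is an assumption. The chance is 1 − (1 − q)^n. Take n = 5 as an illustration, n = 10 as the pilot maximum (20 enrolled, 1:1, all in Group A), and n = 25 for the larger trial. For example, 1 − 0.97⁵ = 0.141.

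**4. Dilution of ITT in the larger trial.** Assume a barred A2 child keeps the 80% flare risk. The A2 risk is then 0.8q + 0.4(1 − q); at q = 5% it is 0.04 + 0.38 = 0.42. Power is by the pooled normal approximation with 23 evaluable per arm.

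| q | n = 5 | n = 10 | n = 25 | A2 risk | Difference | Power |
|---|---|---|---|---|---|---|
| 0 | 0 | 0 | 0 | 40.0% | 40.0 points | 81.2% |
| 1% | 5% | 10% | 22% | 40.4% | 39.6 | 80.4% |
| 2% | 10% | 18% | 40% | 40.8% | 39.2 | 79.6% |
| 3% | 14% | 26% | 53% | 41.2% | 38.8 | 78.8% |
| 5% | 23% | 40% | 72% | 42.0% | 38.0 | 77.1% |

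The number found by planned ECG in A1 is zero at every rate. One barred child is 1/5 = 20% of an A2 arm of 5, and 1/25 = 4% of an arm of 25.

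**The case against.** The strongest reply is that exclusion 7 is worded by history and risk factors, names no ECG result, and is reviewed in every child twice before randomisation. On that reading the ECG is a safety check on the drug, and a child it bars is simply a randomised, untreated participant whom ITT handles correctly. Much of this stands. What remains is that section 8.2 itself calls the ECG screening, that it can bar treatment, and that nothing re-applies exclusion 7 before allocation. A site could do the ECG first at the week-4 visit, since section 8.2 does not fix the order, but footnote e selects children by their group.

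A reader might infer several stronger points that the documents do not support:

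- *Barred A2 children are dropped from the primary analysis.* ITT keeps them. Section 7.2 permits withdrawal for a newly met exclusion in either arm, but does not require it.
- *Children with a prolonged QTc will be dosed.* The pre-treatment ECG protects against this, provided it is done.
- *The pregnancy, C. difficile and laboratory exclusions could be re-applied at week 4 from data already collected.* Footnote d limits the pregnancy test to post-menarchal girls starting methotrexate, footnote c limits C. difficile testing to screening when clinically indicated, and exclusion 15 concerns screening results.
- *Low potassium or magnesium cannot be detected because neither is listed.* Footnote a is not exhaustive (section 8.1 adds urea), so this is minor.

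The addendum also accepts that the pilot cannot support efficacy conclusions, so dilution in the pilot changes no efficacy decision. The feasibility measure and the carry-forward to the full trial are not answered by this.

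**Conclusion.** The point holds in a limited form. As written, eligibility is not reviewed at the visit where children are randomised, and QT prolongation can be found by ECG in A2 but not in A1. The effect is dilution of the primary ITT comparison, one-sided loss from the sets defined by antibiotic intake, and an overstated feasibility count.

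The size depends on a rate that the documents do not give. At an assumed 1–2%, power in the larger trial falls by about 1 to 2 points (81.2% to 80.4% or 79.6%), which is small. At 5% it falls by about 4 points, to 77.1%, and the chance of at least one barred child is 72% with 25 in A2. These power figures assume that a barred child keeps the control-arm flare risk. The finding on the order of steps does not depend on any rate.

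It would go too far to say that an exclusion criterion as such is applied in one arm only: exclusion 7 is reviewed in all children at screening and week 0. Only the ECG check is one-sided.

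**What to change.** 1. Mark the inclusion/exclusion review at week 4 in the Schedule of Activities, and state in section 6.3 that it is completed before the envelope is opened. It re-checks exclusion 7 from the medical history and concomitant-medication review already scheduled. Children who now meet it are not randomised and are followed outside the A1/A2 comparison.
2. State in section 9.3 that any A2 child barred from antibiotics by an ECG after allocation stays in A2 for ITT, and align section 7.1 with this.
3. Optional: if the sponsor accepts one extra non-invasive ECG per A1 child (at most 10 in the pilot), do the baseline ECG in all Group A candidates before allocation. That removes the one-arm loss at the baseline ECG.
4. Reconcile footnote e with section 8.2, which names only A2 for the follow-up ECG, and with section 2.3.3, under which Group C is not randomised. Which groups should have the follow-up ECG is for the sponsor to settle.

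Items 1, 2 and 4 need wording and a short check at an existing visit. The downside is that slightly fewer children may be randomised. Item 3 is the only one that adds a procedure.

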2 INTRODUCTION

2.1 STUDY RATIONALE

Crohn's disease (CD) is a major phenotype of inflammatory bowel disease (IBD) characterized by transmural (often granulomatous and patchy) inflammation throughout the gastrointestinal (GI) tract, most often involving the ileum and colon. Chronic inflammation within the GI tract can cause progressive tissue damage leading to serious complications requiring surgery, including intra-abdominal abscesses, fistulas, and intestinal strictures.¹ CD is highly heterogeneous with respect to age of onset, disease location (i.e. anatomical extent) and behavior (i.e. inflammatory or stricturing/penetrating disease). Disease course is also highly variable among patients with some experiencing chronically active severe disease while others have intermittent periods of clinical remission and disease exacerbation (i.e. 'flares'). Patient responses to therapy are also highly variable, but the reasons for this are not fully understood.

Current treatments for CD aim to not only control symptoms but to maintain clinical remission and mucosal healing (deep remission).² Corticosteroids, enteral nutrition, thiopurines, methotrexate and biologics (such as monoclonal antibodies against tumour necrosis factor- α : 'anti-TNF') are effective to modulate inflammatory activity, but surgery is still frequently required.³

The exact cause of CD is unclear, but current thinking holds that disease results from a defective or inappropriate activation of the mucosal immune system response to commensal gut microbiota, collectively termed the gut microbiome.¹ Certain bacteria can adhere to and invade epithelial cells of the inflamed mucosa and granulomas to replicate inside macrophage phagolysosomes.⁴ Numerous CD susceptibility genes are involved in pathways that govern innate immunity, recognition of bacterial pathogens, and handling of intracellular bacteria.⁵ Diversion of the fecal stream can lead to clinical improvement in medically refractory Crohn's colitis.⁶

The field of microbiome research has grown exponentially over the past several years, catalyzed by the US-led Human Microbiome Project (HMP)⁷ and the European-led MetaHIT⁸ project. Studies using next-generation sequencing and new bioinformatics approaches have begun to characterize fundamental differences in the gut microbiome in children (and adults) with CD versus healthy controls.⁹⁻¹¹ The ileum and colon is densely populated with a variety of metabolically active bacteria that interact with the host immune system. The collective genomic content of the microbiome—the metagenome—has been

estimated to contain at least 100-times more genes than the human genome. The influence of the microbiome on disease pathogenesis and progression in CD is a significant area of research interest, since a breakdown in the balance between protective and harmful bacteria (termed 'dysbiosis') is the current prevailing hypothesis for the development of CD.¹² Animal studies have shown that bacterial load and the composition of bacterial communities can influence both the site and degree of inflammation in the GI tract.^{13,14} Several studies applying microbial profiling and in-depth sequencing techniques to the collective DNA content of gut microbiota (i.e. microbiome) of CD patients have shown distinct microbiome profiles associated with different clinical outcomes or responses to treatment.^{3,15-19}

The probable role for bacteria in triggering disease activity implies that antibiotics could have a role in CD therapy. However, while several meta-analyses support the use of antibiotics in controlling luminal inflammation, results of individual trials are heterogeneous.^{2,20} Recently, a combination of azithromycin/metronidazole has been found to be superior to metronidazole alone for induction of remission and improvement in fecal calprotectin.²¹ However, individual responses to this antibiotic treatment were variable, showing the percentage of clinical response to equal that of remission. This "all or nothing" phenomenon suggests that the effect of antibiotics may depend on the type of microbiota involved and their susceptibility to antibiotics. Antibiotics used in previous trials such as rifaximin are non-absorbable and would be less effective against bacteria that have already translocated into tissue.²¹⁻²³

Recently, the Crohn's Disease Exclusion diet was shown to be associated with comparable efficacy but superior tolerance and maintenance of remission than exclusive enteral nutrition in a randomized controlled trial.²⁴

The purpose for the proposed pilot trial is to determine whether personalized, microbiome-informed administration of an azithromycin/metronidazole antibiotic can improve clinical response to nutritional induction therapy and prolong remission compared to induction therapy alone.

